Specific Aim 3 - The null hypothesis is that chronic sympathetic blockade will not improve inflammation in obese hypertensive subjects. We will measure the percent of circulating T cells that express both CD4 and CD45RO (CD4+ /CD45RO+), at baseline and after nine weeks of treatment with each of the study drugs as in the previous specific aims. Obese hypertensive subjects will be studied twice, at the beginning (BSL) and the end of 9 weeks of treatment with either the sympathetic blocker moxonidine (MOX) and the calcium channel blocker amlodipine (AML). The primary outcome variable will be the change from baseline in the CD8+ /CD45RO+ percentage of circulating T cells. The null hypothesis will be that there is no difference in this outcome in patients treated with moxonidine compared to patients treated with amlodipine. The primary analysis will be to conduct an unpaired t-test on the primary outcome that is similar to that described for Aim 1.a. Secondary analyses to account for a possible skewed distribution of the primary outcome, to adjust for potential confounding variables will also be performed in a fashion that is similar to the analyses for Aim 1.a.

Sample size calculation. We estimated the sample size based on previous studies ((36), figure 9) that have found an increased percentage of CD4+

/CD45RO+ circulation T cells in hypertensive human subjects. They found that hypertensive subjects have 20% more circulating T cells expressing both CD4 and CD45RO as compared to healthy controls. We expect to see a reduction of at least 15 ± 5 percent after 9 weeks of treatment with moxonidine. A decrease of 15% in the moxonidine arm will translate as 45% of CD4+ /CD45RO+ (from 60% at baseline), after 9 weeks of MOX treatment. Assuming that a SD of the difference is 15%, a sample size of 27 subjects per arm would provide 95% power to detect a difference of this magnitude with a=0.05.

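### Aim 3 measures and powers on CD4+/CD45RO+ T cells but names CD8+/CD45RO+ as its primary outcome, so the stated 95% power belongs to a different endpoint

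*Combined protocol and SAP*

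**What the plan says.** All the key text is in section 10.0, Specific Aim 3, and the sample size paragraph that follows it.

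- **Measurement:** "We will measure the percent of circulating T cells that express both CD4 and CD45RO (CD4+ /CD45RO+), at baseline" and again after nine weeks of treatment.
- **Primary outcome:** "The primary outcome variable will be the change from baseline in the CD8+ /CD45RO+ percentage of circulating T cells".
- **Hypothesis:** "The null hypothesis will be that there is no difference in this outcome in patients treated with moxonidine compared to patients treated with amlodipine".
- **Test:** "The primary analysis will be to conduct an unpaired t-test on the primary outcome that is similar to that described for Aim 1.a".
- **Prior data for the sample size:** "hypertensive subjects have 20% more circulating T cells expressing both CD4 and CD45RO as compared to healthy controls".
- **Effect assumed:** "A decrease of 15% in the moxonidine arm will translate as 45% of CD4+ /CD45RO+ (from 60% at baseline), after 9 weeks of MOX treatment".
- **Power:** with an SD of the difference of 15%, 27 subjects per arm are said to give 95% power at an alpha of 0.05. Sidedness is not stated.

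Two other sections touch the subject. The Aim 3 rationale in section 2.0 reports earlier work in which both the CD4+ and the CD8+/CD45RO+ subsets were raised in hypertensive subjects, but it gives no values. Section 6.0 lists blood for flow analysis of immune cells at visit 2, repeated at the end of treatment, and names no subset.

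**The concern.** CD4+ and CD8+ memory T cells are different populations, so two variables are in play within one aim and only one of them is called primary. The words for outcome in the hypothesis and test sentences point back to the CD8+ sentence. An analyst who follows the text literally therefore tests CD8+/CD45RO+, for which there is no power basis. The subset the aim says it measures then has no primary test at all.

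A second analyst could rely on the measurement and sample size text and test CD4+/CD45RO+. Both could claim to have followed the plan, and their results could differ. If the choice is still open when the data are seen, the result can influence it.

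**Working it through.** **1. Which subset each statement concerns**

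| Element of Aim 3 | Subset |
|---|---|
| Measurement sentence | CD4+/CD45RO+ |
| Primary outcome sentence | CD8+/CD45RO+ |
| Null hypothesis and t-test | CD8+/CD45RO+, by reference back |
| Prior data cited for the sample size | CD4+/CD45RO+ |
| Assumed change (60% to 45%) and resulting power | CD4+/CD45RO+ |

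No section reconciles the two.

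**2. The plan's own power figure**

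Inputs, all from the Aim 3 sample size paragraph: difference 60 − 45 = 15 points, SD 15 points, n = 27 per arm, alpha 0.05 (taken as two-sided).

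- Standardized effect: d = 15 / 15 = 1.0.
- Noncentrality: d / √(2/n) = 1.0 / √(2/27) = 3.674.
- Degrees of freedom: 2 × 27 − 2 = 52; critical t = 2.007.
- Power from the noncentral t distribution: 0.950. The normal approximation gives 0.957.

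The 95% reproduces. A one-sided test would give 0.976, so the figure is two-sided. With the 29 evaluable per arm planned for Aim 1a, power would be 0.963. The arithmetic is right, but its inputs are for CD4+/CD45RO+.

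**3. Power for the outcome named as primary**

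The documents give no baseline level, expected change or SD for CD8+/CD45RO+, so d is unknown and power cannot be derived. The range below is an assumption, using the same two-sided t-test with 27 per arm:

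| Assumed d for CD8+/CD45RO+ | Power |
|---|---|
| 1.0 | 95% |
| 0.8 | 82% |
| 0.75 | 77% |
| 0.6 | 58% |
| 0.5 | 44% |
| 0.4 | 30% |

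The 95% carries over only if the CD8+ effect is as large, relative to its SD, as the one assumed for CD4+.

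**4. False-positive chance if either subset could be called primary**

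This assumes that both subsets are tested at 0.05 and that either result could be reported as primary.

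- Independent tests: 1 − (1 − 0.05)² = 1 − 0.9025 = 0.0975.
- Correlated test statistics (bivariate normal, two-sided): 9.5% at correlation 0.3, 9.1% at 0.5, 7.8% at 0.8.

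So 9.75% is the ceiling. Both percentages come from the same blood samples, so some correlation is likely and the true figure would be lower.

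**The case against.** The strongest reply is that this is a one-character slip. Apart from the outcome sentence, every mention of a marker in the Aim 3 text of section 10.0 is CD4+. If CD4+ was meant, the power statement stands and a single digit is corrected. Trial size is untouched either way: section 10.0 fixes 36 enrolled per arm from Aim 1a and applies that number to the other aims.

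That reading is plausible, and the point about trial size is correct. It does not make the text usable as it stands. Section 2.0 names both subsets as raised in hypertension, so CD8+/CD45RO+ is a credible endpoint, and the documents do not settle the intent. The statement in section 10.0 that smaller samples would suffice for Aim 3 also has no support if CD8+ is meant.

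A second objection is that 9.75% does not follow from the plan, which names one outcome and one test. Taken literally, that is a single test at 5%. This is fair. The 9.75% is a conditional worst case that needs both subsets to be tested and the primary chosen afterwards.

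A third is that the documents do not say both subsets will be assayed, because section 6.0 names none. This also stands as a caution. The plan treats each subset as an Aim 3 variable, so it is reasonable to infer that both are obtained, but the sponsor should confirm it.

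**Conclusion.** The concern holds. The primary outcome of Aim 3 is defined on one T-cell subset, while its measurement and power are defined on another. The 95% is correctly calculated for CD4+/CD45RO+ and says nothing about CD8+/CD45RO+, for which no power figure can be supported. The 30% to 95% range rests wholly on assumed standardized effects. The rise in false-positive chance from 5% to at most 9.75% applies only if the choice of subset stays open until results are known.

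The effect is confined to Aim 3, and the enrolment target does not depend on it. It must still be fixed, because the identity of a primary outcome is in doubt and a correction after unblinding would not be credible.

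**What to change.** The sponsor should state, before unblinding, which subset is primary, and align the measurement, outcome and sample size text.

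- **If CD4+/CD45RO+ is intended**, as most of the Aim 3 text suggests: reword the outcome sentence so that the primary variable is the change from baseline in the CD4+/CD45RO+ percentage of circulating T cells, and list CD8+/CD45RO+ as secondary if it is to be reported. The 95% power stands. The cost is one sentence.
- **If CD8+/CD45RO+ is intended**: correct the measurement sentence, replace the sample size inputs with a CD8+/CD45RO+ baseline, expected change and SD and give their source, and restate the power at the planned sample size. The cost is a rewritten paragraph and suitable prior data.

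In both cases the sponsor should confirm which subsets the planned flow analysis will quantify. Extra assay work is not expected, but the documents do not state the panel.

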11.0 Privacy/Confidentiality Issues

All studies will be done by trained personnel in a quiet room, within or adjacent to the Clinical Research Center. Women of child-bearing potential will have a serum pregnancy test to exclude pregnancy immediately before study participation. In order to minimize any potential risk, a physician and a research nurse will be present and monitor all procedures involving the administration of investigational medications. Careful and continuous monitoring of all vital signs during the studies will help minimize potential risks. Blood pressure and heart rate are monitored continuously using non-invasive techniques whenever drugs are infused. Confidentiality will be maintained for the identity of participants in this study except as necessary for oversight by the Secretary of the Department of Health and Human Services or his designated representative. Subjects will be instructed to contact the investigator immediately if they experience any signs of adverse events during withdrawal of medications. Any adverse events will be reported in a timely fashion to the principal investigator. All adverse events will be documented on the Adverse Event form and reported to the IRB, All subjects who have adverse events will be monitored to determine the outcome. The clinical course of the adverse event will be followed according to accepted standards of medical practice, even after the end of the period of observation. To date, no subjects have had adverse events to the procedures described.

12.0 Follow-up and Record Retention

The project will take 5 years, during the first two quarters of the funding period, we will obtain regulatory approvals and develop the database and case report forms. Patient recruitment will start on the third quarter and continue through Year 5. We propose to enroll a total of 72 subjects. We estimate 30% will be screen failures or dropouts. Eligible participants will be studied on the CRC. Since the same patients will participate in aims 1 and 2, the studies on all aims will be conducted simultaneously. Final data analysis and manuscript preparation will be started the fourth year

The research material obtained in this proposal will be recorded data obtained specifically for research purposes. Blood and urine samples will be obtained for screening purposes and for analysis of the various parameters under study. A separate secure database of patient information will be maintained using the REDCap web-based software, a HIPAA compliant secure database. Only investigators listed in this application will have access to research information and will follow IRB and institutional HIPAA guidelines. Both paper and computer files will be saved under lock/password protection.

